**Key Secondary Endpoints** The proximal outcomes of child and caregiver behaviors and sense of competence after the intervention. Key proximal outcomes will be change from baseline (pre-intervention) to 9-weeks (post-intervention) in caregiver sense of competence measured by the Parent Sense of Competence Scale and child behaviors measured by the sum of 4 items from the JERI (Joint Engagement, Attention to Caregiver, Responsiveness to Partner's Communication Bids, Fluency and Connectedness) coded by a trained, reliable coder who is naïve with respect to whether the observation is from baseline our outcome using video-recorded caregiver-child interactions.

**Other Exploratory Endpoints** Additional exploratory outcomes will be change in caregiver ratings from baseline to 9-week in the following measures: a) ADHD-RS ratings of the child's attention; b) Aberrant Behavior Checklist (ABC), including inattention/hyperactivity, social withdrawal, stereotypies, irritability, and inappropriate speech; c) Social Reciprocity Scale-2 (SRS-2) ratings of child's social communication behavior; d) Caregiver Strain Questionnaire (CSQ) ratings of the impact of the child's condition on the family and caregiver and quality-of-life; e) Behavior Rating Inventory of Executive Functions (BRIEF) ratings of child's executive function; and f) Child Behavior Checklist (CBCL) ratings of child behavioral and emotional problems. Change from baseline (pre-intervention) to 16-weeks (8-weeks post-intervention) will be assessed for the VABS-3 Socialization and Communication Subscale Standard Scores.

**Study Population:** ~ 30-35 participants who are between 36 months and <132 months of age with comorbid ASD and ADHD.

- Inclusion criteria**
- Provision of a parent/guardian signed and dated informed consent form.
  - Stated willingness of parent/guardian to comply with all study

procedures and availability for the duration of the study.

- Child is between 36 months and <132 months of age at baseline.
- Child has a confirmed DSM-5 diagnosis of both ASD and ADHD, informed by results of assessments including: an ASD diagnostic assessment (Brief Observation of Symptoms of Autism [BOSA], Autism Diagnostic Observation Schedule, 2nd Edition [ADOS-2], or TELE-ASD-PEDS, and if applicable the Autism Diagnostic Interview - Revised [ADI-R]) and an ADHD diagnostic (a standardized ADHD Diagnostic Interview and the MINI psychiatric diagnostic interview).

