### 1.3 Schedule Of Activities (SoA)

ACTIVITIES	Consent & Diagnostic Confirmation a & Feedback	Baseline/and call with Coach	Coaching W1	Coaching W2	Coaching W3	Coaching W4	Coaching W5	Coaching W6	Coaching W7	Coaching W8	Endpoint Assessments	Remote Follow-up
Typical Week offset from baseline A	prior	0	1	2	3	4	5	6	7	8	9	16
Informed consent	X											
Demographics, ACE subject Med Hx, ACE Fam Hx, Intervention Hx,  Spence	X											
Diagnostic & Cognitive testing	X											
ESDM-informed caregiver coaching		Brief call	X	X	X	X	X	X	X	X		
P-ESDM Caregiver Self-Monitoring checklist**			X	X	X	X	X	X	X	X		
ESDM coach fidelity *			*	*	*	*	*	*	*	*		
ESDM caregiver fidelity		X	X	X	X	X	X	X	X	X	X	
Remote PCIT												
JERI coding of child/ caregiver items		X									X	
Qualitative Interview											X	
AIM, IAM, FIM											X	
Caregiver Sense of Competence Scale		X									X	X
App S2K		X									X	X
ABC		X					X				X	X
Vineland-3 parent questionnaire	X										X	X
CBCL	X										X	X
ADHD-RS-parent	X										X	X
SRS-2	X	(X) +									X	X
Caregiver Strain Questionnaire		X									X	X
Condensed (non-ASD) Med Hx  , AE's, Con Meds,		X	X	X	X	X	X	X	X	X	X	
BRIEF	X	(X) +									X	

A: no strict window for visits, but ideally post-baseline visits should be done within ± 7 days (relative to visit each time point from baseline); \*: done once randomly

during sessions 2-8; \*\*: completed by caregiver and coach; **Green text: measures acquired in ARC and in P3**; (X)+: only needs to be done if baseline done more than 3 months prior; 2: non ASD med history only done at baseline visit & diagnostic confirmation is informed by ARC assessments. Participants typically begin study participation within 1-3 months of completing the ARC evaluation (if the participant is eligible). However, we also expect that in some situations, (e.g., due to the COVID-19 pandemic) there may be a delay between the ARC evaluation and participation in the A+ Treatment/Feasibility sub-study. If this happens, the following assessments and/or parent-report forms may be repeated:

- If > 2 years since ARC completion: ASD diagnostic assessment (e.g., BOSA, ADOS, TELE-ASD-PEDS) and cognitive assessment (e.g., WPPSI/WISC, DAYC-2, DAS-2, Mullen)
- If > 6 months since ARC completion: CBCL
- If > 3 months since ARC completion of: SRS-2, VABS, ADHD-RS parent form

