Aim 2: Assess proximal and distal child and caregiver outcomes. Both proximal and distal outcomes will be measured. Key proximal outcome will be change from baseline (pre-intervention) to 9-weeks (immediately post-intervention) in caregiver sense of competence measured by the Parent Sense of Competence Scale and child behaviors measured by the sum of 4 items from the JERI (Joint Engagement, Attention to Caregiver, Responsiveness to Partner's Communication Bids, Fluency and Connectedness) coded by a trained, reliable coder who is naïve with respect to whether the observation is from baseline our outcome using video-recorded caregiver-child interactions.

Hypothesis: we will detect proximal changes in child and caregiver interactions and caregiver sense of competence.

Exploratory Outcome: In this exploratory outcome we will assess change in caregiver ratings from baseline to 9-week in the following measures: a) ADHD-RS ratings of the child's attention; b) Aberrant Behavior Checklist (ABC), including inattention/hyperactivity, social withdrawal, stereotypies, irritability, and inappropriate speech; c) Social Reciprocity Scale-2 (SRS-2) ratings of child's social communication behavior; d) Caregiver Strain Questionnaire (CSQ) ratings of the impact of the child's condition on the family and caregiver and quality-of-life; e) Behavior Rating Inventory of Executive Functions (BRIEF) ratings of child's executive function; and f) Child Behavior Checklist (CBCL) ratings of child behavioral and emotional problems. Change from baseline (pre-intervention) to 16-weeks (8-weeks post-intervention) will be assessed for the VABS-3 Socialization and Communication Subscale Standard Scores.

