### 3 OBJECTIVES AND ENDPOINTS

OBJECTIVES	ENDPOINTS
PRIMARY	
Determine implementation outcomes including acceptability, appropriateness, feasibility, and fidelity.	Acceptability, appropriateness, and feasibility will be quantitatively and qualitatively assessed using 4-item, pragmatic scales and individual stakeholder interviews.  Fidelity of intervention delivery, will be monitored using an adapted version of the Parent Early Start Denver Model (P-ESDM) Caregiver Fidelity Rating System.
SECONDARY	
Determine proximal changes in child and caregiver interactions and caregiver sense of competence	A key proximal outcome will be change from baseline (pre-intervention) to 9-weeks (immediately post-intervention) in caregiver sense of competence measured by the Parent Sense of Competence Scale and child behaviors measured by the sum of 4 items from the JERI (Joint Engagement, Attention to Caregiver, Responsiveness to Partner’s Communication Bids, Fluency and Connectedness).
Other Exploratory behavioral outcomes at 9 weeks and 16 weeks	
Assess core ASD social	• Social Responsiveness Scale-2 (SRS-2)(66-68)

OBJECTIVES	ENDPOINTS
functions, ADHD symptoms, symptoms and adaptive functioning	
 
• Aberrant Behavior Checklist-2 (ABC)(69, 70)
 
• ADHD-RS
 
• VABS-3
 

Assess other aspects of attention and executive function	
 
• Behavioral Rating Inventory of Executive Function (BRIEF)(77, 78)
 

Other Relevant Behaviors	
 
• Child Behavior Checklist (CBCL)(79)
 

Caregiver functioning & attitudes toward treatment	
 
• Caregiver Strain Questionnaire (CSQ)(83, 84)
 

Safety assessments	
 
• Treatment emergent adverse effects assessed based on spontaneous report from parent/caregiver
 

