#### 4.4 End of Study Definition

A participant is considered to have completed the study if he or she has completed the endpoint assessments of all phases of the study or has been withdrawn from both treatment and assessments in the study. If a participant chooses to stop behavioral treatment in the study before endpoint assessments, he or she will be requested to complete them on schedule if at all possible. The follow-up visit at 16 weeks following baseline is optional.

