- **Aberrant Behavior Checklist – 2nd Edition Community Version (ABC)** is a parent report measure that was initially developed for use with intellectually disabled children and adults in residential settings but has been validated for use with individuals with ASD living in the community. Reference values are available from large samples of individuals with ASD. The ABC includes 5 subscales: irritability, attention, lethargy/social withdrawal, repetitive behaviors, and abnormal language. Each of the 40 items is rated from 0 – not at all a problem to 3 – very much a problem. Respondents are asked to rate behaviors in comparison to typically developing individuals. The ABC will be obtained at baseline and endpoint.
- **Behavior Rating Inventory of Executive Function (BRIEF)** The BRIEF is a caregiver report measure that assesses age appropriate executive function behaviors for children. The preschool BRIEF is for children between 3 years and 5 years 11 months and the BRIEF-2 is designed for children 6 and

older. The same version of the BRIEF will be used at baseline and endpoint to assess changes over time. The following domains will be examined: inhibition, shifting, emotional control, working memory and planning.

- **Caregiver Strain Questionnaire (CSQ)** The CSQ is a caregiver completed measure with 21 questions assessing the impact of a child with a developmental disorder or behavioral disorder on the caregiver and the rest of the family. Questions are rated on a 5 point scale from not at all a problem to very much a problem. In the original version one item is reverse scored. We will use a version in which the question is rephrased to avoid reverse scoring. The scale has 3 subscales: objective, internalizing and externalizing. It takes about 5 minutes to complete.

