- **Child Behavior Checklist (CBCL)** The CBCL is a caregiver- completed scale that assesses problem behaviors using a 3 point scale (*not true, somewhat or sometimes true, and very true or often true*) over the prior two months. The preschool version is designed for children 1.5 to 5 years and contains 99 items. The school age version is designed for children 6-17 and contains 118 items. The behavioral domains that are assessed include Emotionally Reactive; Anxious/Depressed; Somatic Complaints; Withdrawn; Attention Problems; Aggressive Behavior and, in the older version, sleep problems. There are also DSM-oriented scales that are consistent with DSM-5 diagnostic categories. Depressive Problems; Anxiety Problems; Autism Spectrum Problems; Attention Deficit/Hyperactivity Problems; Oppositional Defiant Problems. The scale is standardized to provide a mean T score of 50 with a standard deviation of 10. Higher scores reflect more impairment. It has been studied in samples of both school-aged and preschool children with ASD, other psychiatric disorders and typical development(85, 86). It takes about 15 min to complete. <http://www.aseba.org/preschool.html>
- **Social Responsiveness Scale- Revised (SRS-2)** is a parent report version characterizing various social and repetitive behaviors associated with ASD. The scale's 65 items are rated between 1 and 4 and typically can be completed within 10 minutes. It is designed for use in children between the ages of 2 ½ – 18 years. It contains subscales assessing social awareness, social cognition, social communication, social motivation, and restricted and repetitive behaviors. The measure has been standardized on a large sample including individuals with typical development and demonstrated to be distributed along a continuum. Threshold scores suggestive of ASD have been determined separately for boys and girls. Caregivers of participants between ages 2.5 and <4 years will receive the Preschool SRS-2, and those ages 4 and above will be asked to complete SRS-2 School age version. The SRS will be obtained at baseline and endpoint.

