### 9.3.8 Exploratory analyses

Additional Exploratory proximal and distal outcomes of interest include: a) caregiver ADHD-RS ratings of the child’s attention. b) Aberrant Behavior Checklist (ABC), including inattention/hyperactivity, social withdrawal, stereotypies, irritability, and inappropriate speech; c) Social Reciprocity Scale-2 (SRS-2) ratings of child’s social communication behavior; d) Caregiver Strain Questionnaire (CSQ) ratings of the impact of the child’s condition on the family and caregiver and quality-of-life; e) Behavior Rating Inventory of Executive Functions (BRIEF) ratings of child’s executive function; and f) Child Behavior

Checklist (CBCL) ratings of child behavioral and emotional problems. Our analysis will focus on graphical displays, which will be complemented by appropriate inferential statistical procedures. For the graphical displays, we will visualize the distribution of proximal and distal outcome measures in histograms to better understand the shape and spread of the distribution of each. In terms of inference, between group change at proximal and distal time points will be based on between group t-tests or, if the assumptions are found to be untenable, the Mann-Whitney U test. Whilst statistical inference is valuable, we anticipate that we will elicit most information through careful data visualization. Change from baseline (pre-intervention) to 16-weeks (8-weeks post-intervention) will be assessed for the VABS-3 Socialization and Communication Subscale Standard Scores.

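### Section 9.3.8 prescribes independent-sample tests of between-group change for the exploratory outcomes of a one-group trial and names no groups

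*Combined protocol and SAP*

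**What the plan says.** **Test rule.** Section 9.3.8 lists six caregiver-rated outcomes (ADHD-RS, ABC, SRS-2, CSQ, BRIEF, CBCL). It puts graphics first and then says that inference on "between group change at proximal and distal time points will be based on between group t-tests", or on the Mann-Whitney U test if assumptions fail. No grouping variable is given there.

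**Design.** Sections 6.1.3 and 6.3 describe one open intervention for all children, without randomisation. Section 9.2 has one analysis population, made up of all participants.

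**Endpoint.** The synopsis says "Additional exploratory outcomes will be change in caregiver ratings from baseline to 9-week in the following measures". Section 2.3 agrees: "In this exploratory outcome we will assess change in caregiver ratings from baseline to 9-week in the following measures". Both give week 16 for the Vineland-3 (VABS-3) Socialization and Communication scores, as does section 9.3.8.

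**Related rules.** Section 9.3.3, in its paragraph on Aim 2 data analysis, sets a paired t-test or Wilcoxon signed-rank test for pre-post change and uses a Vineland-3 score as its example. Section 9.3.7 allows subgroup analyses only without inference, because the subgroups are expected to be too small.

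**Timing.** The section 3 heading reads "Other Exploratory behavioral outcomes at 9 weeks and 16 weeks". The schedule in section 1.3 marks five of the six ratings at week 16 (for example the row "ADHD-RS-parent"), all but BRIEF. Section 8 says "The ABC will be obtained at baseline and endpoint" and "The SRS will be obtained at baseline and endpoint". Section 4.4 adds: "The follow-up visit at 16 weeks following baseline is optional".

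**The concern.** A between-group t-test compares separate sets of children. The stated endpoint is change within the same child, and the design supplies no second set of children to compare with. An analyst following 9.3.8 must therefore invent the groups, or treat baseline and follow-up as if they came from different children.

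The first choice answers a question that the endpoint does not ask, and attaches p-values to subgroups that 9.3.7 keeps descriptive. The second throws away the correlation between a child's two scores, and with it precision that a small study can ill afford. Leaving the choice open also lets it be made after the data have been seen.

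**Working it through.** The documents give no alpha, power, standard deviation or correlation for these outcomes, so there is no stated figure to reproduce. The check is mainly a comparison of text, with two illustrations.

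**1. What could group mean?**
- *Subgroup.* Candidates are age, gender and IQ (section 9.3.1) or ADHD-medication status (section 6.1.1). None is linked to 9.3.8. The test would be valid for a difference in change between two kinds of children, but it would not estimate mean change in the cohort, and 9.3.7 excludes inference on it.
- *Time point.* This is the less natural reading. The observations are paired, so an independent-sample test is the wrong one, and it departs from 9.3.3.

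Each conflict belongs to one reading. Neither reading gives a test that fits both the endpoint and the rest of the plan.

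**2. Number of completers.** The target is 30-35 and attrition about 15% (section 5.5): 30 × 0.85 = 25.5 and 35 × 0.85 = 29.75, rounded down to 25 and 29. Week 16 is optional and may have fewer.

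**3. Subgroup reading, illustrated.** Assumptions: two-sided alpha 5%, 80% power, equal change-score SDs in the two groups, and the splits shown. The detectable difference is the δ for which a noncentral t variable with a + b − 2 degrees of freedom and noncentrality δ·sqrt(ab/(a + b)) exceeds the 97.5% point of t with probability 0.80.
- 25 completers: 1.17 change-score SD (split 12/13) or 1.25 (8/17).
- 29 completers: 1.08 (14/15) or 1.17 (9/20).

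Differences this large bear out the view in 9.3.7 that subgroups are too small for inference.

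**4. Time-point reading, illustrated.** With equal pre and post variance σ² and correlation r, the unpaired SE of the mean change is sqrt(2σ²/n) and the paired SE is sqrt(2σ²(1 − r)/n). The ratio is 1/sqrt(1 − r), whatever the n. The table adds the actual size of a nominal 5% independent t-test and the power for an assumed shift of 0.5 SD, all at n = 25. Size and independent-test power come from 40,000 simulated normal datasets; paired power comes from the noncentral t.

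| r (assumed) | SE ratio | Actual size | Power, independent | Power, paired |
|---|---|---|---|---|
| 0.3 | 1.20 | 0.020 | 0.395 | 0.527 |
| 0.5 | 1.41 | 0.007 | 0.381 | 0.670 |
| 0.7 | 1.83 | 0.001 | 0.356 | 0.872 |

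At n = 29 and r = 0.5 the powers are 0.458 and 0.739. With positive correlation the error is therefore conservative: it hides change and does not create false positives.

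**5. Time points.** The explicit endpoint definitions give week 9 for the six ratings. The schedule also collects ADHD-RS, ABC, SRS-2, CSQ and CBCL at week 16, and no passage says plainly whether those data are analysed. The section 8 sentences on ABC and SRS-2 mention baseline and endpoint only, which differs from the schedule.

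**The case against.** The best defence is that the damage is small. Section 4.2 says that the study is not meant to evaluate efficacy, section 9.3.8 expects most of its information from visual displays, and section 9.3.1 promises a final SAP signed before database lock, where groups could be defined. All of this limits the consequence. It does not repair the sentence, which as written points to a test that does not suit the design.

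Three stronger readings are tempting, and the documents do not support them.

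- *That 9.3.8 contradicts both 9.3.3 and 9.3.7 at once.* Under the subgroup reading, 9.3.3 and 9.3.8 estimate different quantities and both could be run. The clash with 9.3.3 arises only under the time-point reading. It also relies on 9.3.3, headed for secondary endpoints, reaching the six ratings. The Aim 2 label, the coverage of each outcome measure and the Vineland-3 example make that likely, but it remains an inference.
- *That the documents flatly disagree on week 16.* The section 3 heading covers a block that includes the Vineland-3, so it can be read as week 9 for the ratings and week 16 for the Vineland-3. Collecting a measure at week 16 does not commit the plan to testing it. Only the section 8 sentences on ABC and SRS-2 plainly differ from the schedule.
- *That subgroup testing widens the confidence interval by some factor.* An interval for a difference in change and an interval for mean change describe different quantities, so their ratio measures no loss.

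**Conclusion.** The point stands as a minor defect. The test sentence in 9.3.8 is wrong for a one-group trial whose exploratory outcomes are changes within child; it does not merely lack detail. This conclusion rests on the text alone.

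The size is illustrative. Under the time-point reading the standard error is 1.41 times too large at an assumed r of 0.5 with equal variances. Under the subgroup reading, detectable differences are about 1.1 to 1.25 change-score SD for the assumed splits, alpha and power. Primary and secondary analyses are unaffected, and nothing here suggests inflated false-positive findings.

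**What to change.** Replace the test sentence in 9.3.8 with the paired rule of 9.3.3: mean within-child change with 95% CI, a paired t-test or Wilcoxon signed-rank test, and the number of pairs. Apply it at the time points in the endpoint definitions, namely week 9 for the six ratings and week 16 for Vineland-3 Socialization and Communication. If a contrast by age, gender, IQ, medication status or another factor is wanted, name the groups and report it descriptively without a test, in line with 9.3.7.

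Separately, state whether the week-16 data for ADHD-RS, ABC, SRS-2, CSQ and CBCL are analysed, and reconcile the section 8 timing of ABC and SRS-2 with the schedule.

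The cost is one replaced sentence, one added statement on week 16 and two timing sentences aligned, all carried into the final SAP before it is signed. No new data or participants are needed.

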## 10 SUPPORTING DOCUMENTATION AND OPERATIONAL CONSIDERATIONS

### 10.1 Regulatory, Ethical and Study Oversight Considerations

#### 10.1.1 Informed consent process

**Consent/Assent Provided to Participants.** Consent forms describing in detail the study intervention, study procedures, and risks are given to the participant's caregiver and documentation of informed consent is required prior to starting intervention/administering study intervention. Informed assent is not required of the participants due to their developmental status. DUHS IRB approved informed consent documents will be used for the preliminary screening study (A+ Assessment) and this study (A+ Treatment). These materials will be provided to the participants' caregivers when they express interest in the study and will be discussed with them as described below.

**Consent Procedures and Documentation:** Informed consent is a process that is initiated prior to the individual's agreeing to participate in the study and continues throughout the individual's study participation. Consent forms and consent procedures will be Institutional Review Board (IRB)-approved. The participant's caregiver(s) will be asked to read and review the document with sufficient time allowed prior to meeting with study staff. If the caregiver is still interested in participating or has questions that may influence his/her willingness to participate, the study coordinator and/or co-investigator or one of the study physicians will explain the research study to the participant and answer any questions that may arise. A verbal explanation will be provided in terms suited to the caregiver's comprehension of the purposes, procedures, and potential risks of the study and of their and their child's rights as research participants. A study physician will always be available to potential participants' caregivers to answer any questions. The caregiver will be encouraged to discuss the study with their family or their child's current providers prior to agreeing to participate.

If the potential participant's caregivers want the child to participate in the study, the caregiver(s) will sign the informed consent document prior to any procedures being done specifically for the study. Participants and their caregivers will be informed that participation is voluntary and that they may withdraw from the study at any time, without prejudice. A copy of the signed informed consent document will be given to the participants for their records. The informed consent process, including the date the documents are signed, will be conducted as per existing Guidance Documents and study MOPs, and documented in the source documents, before the participant undergoes any study-specific procedures. REDCap will be utilized to conduct and document the consent process remotely. A teleconference meeting will be set up to review the consent form with the parent prior to signing the eConsent electronically. The consent process with staff, coaches and/or clinicians who elect to participate in the Qualitative Interview and AIMS-IAM-FIM survey, will be done by trained team

members who are not that person's supervisor or mentor, in order to minimize bias. Voluntariness will be stressed throughout the process.

---

